#### **3.2. Visits schedule**

All subjects will complete screening, on-treatment, and post treatment assessments.

Screening assessments will be completed within 30 days of the Baseline/Day 1 visit, 42 days if liver biopsy is required.

All subjects will complete the following study visits: Screening, Baseline/Day 1, on-treatment visits at Weeks 2, 4, 8 and 12 (for all patients) and weeks 20 and 24 (for those patients receiving 24 weeks of Harvoni® treatment).

Visits	Screening	Baseline / Day 1	Week 2	Week 4	Week 8	Week 12	Week 20	Week 24
12 weeks (Harvoni® or Epclusa®) treatment arm	X	X	X	X	X	X		
24 weeks (Harvoni®) treatment arm	X	X	X	X	X	X	X	X

All subjects will complete post treatment Week 4, 12 and 24 visits.

The assessments performed at each visit are described in Section 6 and shown in Appendix 1.

### 3.3. Virologic Response-Based Stopping Criteria

The following on-treatment virologic response-based treatment stopping criteria will be utilized:

- Confirmed HCV RNA  $\geq$  LLoQ after 2 consecutive HCV RNA  $<$  LLoQ.
- Confirmed  $>1$  log10 increase in HCV RNA from on-treatment nadir.
- HCV RNA  $\geq$  LLoQ through 8 weeks of treatment.

Confirmation should be performed as soon as possible and must occur no later than 2 weeks after an initial observation indicating virologic failure during the on-treatment phase.

All subjects who terminate treatment early will complete the early termination (ET) visit and post treatment 12 and 24 visits.

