**Study Procedures/Frequency:**

Screening assessments will be completed within 30 days of the Baseline/Day 1 visit. The screening window can be extended to 42 days for subjects requiring liver biopsy or additional HCV genotype testing.

All subjects will complete the following study visits: Screening, Baseline/Day 1, on-treatment visits at the end of Weeks 2, 4, 8 and 12 . Subjects who were already enrolled in the study and receiving 12 weeks treatment with Harvoni® will complete the same visits and schedule of events as subjects receiving Epclusa® (detailed in the current protocol version 2). Subjects that receiving 24 weeks treatment with Harvoni® will also complete treatment visits at week 20 and 24. All subjects will complete the post treatment Week 4, 12 and 24 visits.

Screening assessments will include physical examination, medical history, height, weight, vital signs, 12-lead ECG, adverse events related to screening procedures,

concomitant medications, safety laboratory tests (including hematology, chemistry, and coagulation), HCV genotype and HCV RNA, serology (HIV, HCV, HBV), assessment of the presence or absence of cirrhosis, screening for hepatocellular carcinoma if cirrhosis is present, serum  $\beta$ -hCG (females of child bearing potential only), IL28B genotyping, urinalysis, analysis of cryoglobulinemia measuring cryoglobulins, analyzing cross reactive idiotypes, analysis of complement, HCV core ELISA and FACS (appendix 1).

On-treatment assessments include adverse events (AEs), concomitant medications, study medication pill count, physical examination, weight, vital signs, safety laboratory tests (hematology, chemistry, coagulation), HCV RNA (after Baseline/Day1), urine pregnancy tests (females of child bearing potential only), urinalysis, analysis of cryoglobulinemia measuring cryoglobulins, analyzing cross reactive idiotypes, analysis of complement, HCV core ELISA and clonality/lymphoproliferation / FACS (appendix 1).

Post treatment assessments include AEs, concomitant medications, vital signs, safety laboratory tests, HCV RNA, urine pregnancy tests (females of child bearing potential only) and analysis of cryoglobulinemia measuring cryoglobulins, analyzing cross reactive idiotypes, analysis of complement, HCV core ELISA and clonality/lymphoproliferation / FACS (appendix 1).

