### **3.5. Treatment Discontinuation Criteria**

Study drug(s) must be discontinued in the following instances:

- Unacceptable toxicity, as defined in Section 7 of the protocol, or toxicity that, in the judgment of the investigator, compromises the ability to continue study-specific procedures or is considered to not be in the subject's best interest.
- Intercurrent illness that would, in the judgment of the Investigator, affect assessments of clinical status to a significant degree.
- Pregnancy of female subject during the study
- Lack of efficacy (virologic failure) as defined in Section 3.3 and Section 3.4.
- Significant protocol violation.
- Subject request to discontinue for any reason; it is important to determine whether the withdrawal of consent is primarily due to an AE, lack of efficacy or other reason.
- Discontinuation of the study at the request of Gilead Sciences, principal investigator, regulatory agency or an Institutional Review Board (IRB).

All subjects who terminate early will be asked to complete the (ET) visit and post treatment Week 12 visits and week 24.

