### **6.2.2. Treatment assessments (week 2 +/-3 days)**

The following procedures/assessments are to be completed at the end of Week 2.

- Perform a detailed medical history
- Assessment of AEs and concomitant medications
- Pregnancy prevention counseling and confirmation of contraception
- Obtain body height and weight
- Obtain vital signs (resting blood pressure, pulse and temperature)
- Perform complete physical examination, including vasculitis, joint, neuropathy examination and sicca syndrome (for subjects with Sicca syndrome)
- Vasculitis activity score (Birmingham vasculitis score) for subjects with vasculitis.
- Glomerulonephritis evaluation (urine sample and serum creatinine sample) for subjects with glomerulonephritis
- ACR20-70 score (for subjects with Rheumatoid arthritis). This score includes a physical exam, a HAQ and a blood sample to evaluate ESR or CRP.
- Obtain blood samples for:
  - Hematology profile
  - Chemistry profile

- Analysis of cryoglobulinemia measuring cryoglobulins, analyzing cross reactive idiotypes, analysis of complement and HCV core ELISA.
- Obtain urine sample for:
  - Urinalysis and urine creatinine
- Subject completes Health Assessment Questionnaire
- Review study drug compliance and drug administration instructions with subject

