#### **6.4.7. Viral RNA Sequencing / Phenotyping Sample**

Plasma samples will be collected at Baseline/Day 1 and each visit thereafter for viral sequence analysis. At any unscheduled visit initiated for the purpose of confirming virologic breakthrough, a viral sequence analysis plasma sample must be collected.

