## 12. APPENDICES

- Appendix 1a. Study procedures and study visits table.
  
- Appendix 1b. Laboratory tests per visits table
  
- Appendix 2. Common Terminology Criteria for Adverse Events (CTCAE). GSI grading scale for severity of adverse events and laboratory abnormalities.
  
- Appendix 3. Pregnancy Precautions, definition for female of childbearing potential and contraceptive requirements.
  
- Appendix 4. Epclusa® patient information.
  
- Appendix 5a. Epclusa package insert.
  
- Appendix 5b. Harvoni® patient package insert.
  
- Appendix 6. Birmingham vasculitis score.
  
- Appendix 7. Health Assessment Questionnaire (HAQ-DI)
  
- Appendix 8. Visual Analog Scale (VAS)

---

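### Section 6.2.2 lists no Week 2 HCV RNA, against the natural reading of the Synopsis; a site following Section 6.2 could first meet stopping criterion 1 at the end of a 12-week course

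*Combined protocol and SAP*

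**What the plan says.** Section 3.3 gives three on-treatment virologic stopping criteria. Criterion 1 is a confirmed HCV RNA at or above the "LLoQ after 2 consecutive HCV RNA" results below it. Criterion 2 is a confirmed rise of more than 1 log10 from the on-treatment nadir. Criterion 3 is HCV RNA at or above LLoQ through 8 weeks. Confirmation "must occur no later than 2 weeks after an initial observation indicating virologic failure". Section 3.5 makes stopping compulsory, naming among its grounds "Lack of efficacy (virologic failure) as defined in Section 3.3 and Section 3.4".

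The visit lists in Section 6.2 place HCV RNA at Week 4 (6.2.3), Week 8 and, for 24-week courses, Week 20 (6.2.4), and end of treatment (6.2.5). Section 6.2.2 opens "The following procedures/assessments are to be completed at the end of Week 2" and then lists hematology, chemistry and the cryoglobulinemia panel with HCV core ELISA. It does not list HCV RNA.

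The Synopsis, under Study Procedures/Frequency, has one pooled list of on-treatment assessments. It includes "safety laboratory tests (hematology, chemistry, coagulation), HCV RNA (after Baseline/Day1), urine pregnancy tests". Section 3.2 refers the reader to Section 6 and Appendix 1 for the assessments at each visit. Section 12 names "Appendix 1b. Laboratory tests per visits table", but the table itself is not in the text reviewed.

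**The concern.** Criterion 1 needs a run of three results: two below LLoQ, then one at or above it. The number of on-treatment draws therefore decides when the criterion can first apply. With no Week 2 draw, a 12-week course has three scheduled results, and the third is the end-of-treatment sample. A compulsory stopping rule would then apply only when treatment is finishing anyway.

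Section 3.1 gives 12 weeks of treatment to every patient enrolled under version 2, so this is the standard course. At stake is up to four weeks of continued dosing in a patient whose virus has returned at a low level. If the Synopsis does intend a Week 2 draw, the problem is that 6.2.2 leaves it out, and staff working from that list would not order it.

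**Working it through.** **Inputs.** On-treatment visits at Weeks 2, 4, 8 and 12 (Section 3.2), nominally Days 14, 28, 56 and 84 (7 × week). A 12-week course is 84 days (Section 5.2.2). Windows are ±7 days at Weeks 4, 8 and end of treatment (6.2.3 to 6.2.5). Confirmation takes at most 14 days (Section 3.3).

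**Criterion 1.** The earliest trigger is the third HCV RNA draw. Dosing left = 84 − trigger day.

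| Schedule, 12-week course | First three draws | Earliest trigger | Dosing left at trigger | After a 14-day confirmation |
|---|---|---|---|---|
| Section 6.2 as listed | Weeks 4, 8, 12 | Day 84 (earliest in window, Day 77) | 84 − 84 = 0 days (at most 84 − 77 = 7) | None: 84 + 14 = Day 98, or 77 + 14 = Day 91 |
| With a Week 2 draw | Weeks 2, 4, 8 | Day 56 (Days 49 to 63) | 84 − 56 = 28 days (21 to 35) | 28 − 14 = 14 days (7 to 21) |

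The second row holds only for patients below LLoQ at both Weeks 2 and 4. A patient still at or above LLoQ at Week 2 gains nothing on criterion 1.

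**Criteria 2 and 3.** A rise from an on-treatment nadir needs two on-treatment values. On the Section 6.2 lists, criterion 2 can first be met at Week 8, with 84 − 56 = 28 days left. With a Week 2 draw it could be met at Week 4, with 84 − 28 = 56 days left. Criterion 3 is judged at Week 8 on either schedule.

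**What is left uncovered at Week 8 on the Section 6.2 lists.**
- A patient at or above LLoQ at both Weeks 4 and 8 meets criterion 3.
- A patient below LLoQ at Week 4 who then rises by more than 1 log10 to a Week 8 value at or above LLoQ meets criterion 2, once confirmed.
- A patient below LLoQ at Week 4 and at or above it at Week 8, with a rise of 1 log10 or less, meets neither. Criterion 1 does not apply either, because only one earlier result is below LLoQ.

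The width of that gap depends on the value assigned to a result below LLoQ, which the protocol does not give. The upper edge is 10 × the assigned value. If LLoQ is assigned, the gap runs from 1 to 10 × LLoQ. If LLoQ/2 is assigned, it runs from 1 to 5 × LLoQ. At LLoQ/10 or lower there is effectively no gap. These assignments are assumptions.

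**24-week course (168 days).** If Week 12 is not sampled, the third draw is Week 20 (Day 140), leaving 168 − 140 = 28 days. If Week 12 is sampled, it is Day 84, leaving 168 − 84 = 84 days. Criterion 1 works on either reading.

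**The case against.** The strongest reply is that the plan probably does intend a Week 2 draw. In the Synopsis list, HCV RNA is the only item with a visit-timing qualifier, and the one visit it excludes is Baseline. Section 6.2.1 agrees, since it lists no HCV RNA on Day 1. The Section 6 lists are also demonstrably incomplete. Section 6.4.7 says "Plasma samples will be collected at Baseline/Day 1 and each visit thereafter for viral sequence analysis", yet none of the lists in 6.2.1 to 6.2.5 includes that sample. Silence in 6.2.2 is therefore weak evidence that no Week 2 RNA was planned. Appendix 1b may list one, and its absence from the text reviewed is not a fault in the plan.

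This stands, and it limits the claim. A reader might infer that the trial has no Week 2 HCV RNA and that criterion 1 is dead as designed. The documents do not support that. They show a conflict between 6.2.2 and the natural reading of the Synopsis, with an operational effect for anyone who works from 6.2.2. The Synopsis does not fully resolve the conflict either: its pooled list also names coagulation, urine pregnancy tests and clonality/FACS, and 6.2.2 lists none of these at Week 2.

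The second reply is that little depends on it, because criteria 2 and 3 act at Week 8. That is largely right and is why the point is minor. Section 6.4.7 also foresees extra visits: "At any unscheduled visit initiated for the purpose of confirming virologic breakthrough, a viral sequence analysis plasma sample must be collected". Such a visit follows a breakthrough already suspected, however, and does not supply the missing scheduled result.

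**Conclusion.** The point holds as a minor inconsistency with a practical consequence. If Section 6.2 is followed as written, criterion 1 in a 12-week course can first be met at the end-of-treatment visit, with 0 days of dosing left nominally and at most 7. The uncovered case is narrow: below LLoQ at Week 4, at or above it at Week 8, and a rise of 1 log10 or less.

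The conclusion depends on sites working from the Section 6.2 lists. If Appendix 1b already shows a Week 2 HCV RNA and sites follow it, only an editorial omission in 6.2.2 and loose Synopsis wording remain. The documents give no frequency for the uncovered pattern, so no expected number of patients can be stated.

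A reader might also infer that the primary virologic results or patient safety are compromised. They are not: SVR is measured after treatment, at visits that all list HCV RNA, and the toxicity stopping rules in Section 7.2 do not use it.

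**What to change.** - Add HCV RNA to the Week 2 blood samples in Section 6.2.2.
- In the Synopsis, replace the general timing phrase with named visits: Weeks 2, 4, 8 and 12, plus Weeks 20 and 24 for 24-week courses.
- Make Appendix 1b match. If it already lists Week 2, only the first two edits are needed.

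Section 3.3 needs no change. The cost is one added line, one clarified phrase and about 10 assays, one for each of the ten patients in Section 4.1. No visit or venipuncture is added, because 6.2.2 already draws blood at Week 2. The assay cost is the only downside.

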### **3.4. Cryoglobulinemia Response-Based Stopping Criteria**

The following on-treatment response-based treatment stopping criteria will be utilized:

- Unacceptable side effect of the drug (i.e. hypersensitivity reaction, abnormal liver function tests; gastrointestinal side effects).
- Paradoxical effect on the disease manifestations (i.e. increased of systemic vasculitis, renal failure).

### **3.5. Treatment Discontinuation Criteria**

Study drug(s) must be discontinued in the following instances:

- Unacceptable toxicity, as defined in Section 7 of the protocol, or toxicity that, in the judgment of the investigator, compromises the ability to continue study-specific procedures or is considered to not be in the subject's best interest.
- Intercurrent illness that would, in the judgment of the Investigator, affect assessments of clinical status to a significant degree.
- Pregnancy of female subject during the study
- Lack of efficacy (virologic failure) as defined in Section 3.3 and Section 3.4.
- Significant protocol violation.
- Subject request to discontinue for any reason; it is important to determine whether the withdrawal of consent is primarily due to an AE, lack of efficacy or other reason.
- Discontinuation of the study at the request of Gilead Sciences, principal investigator, regulatory agency or an Institutional Review Board (IRB).

All subjects who terminate early will be asked to complete the (ET) visit and post treatment Week 12 visits and week 24.

### **3.6. Discontinuations**

Subjects discontinuing treatment prior to completion of the assigned dosing period should complete an Early Termination (ET) visit (see Section 6.2.7). All subjects who terminate treatment early will complete the Early Termination (ET) visit and post treatment 12 and 24 visits.

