## 6. STUDY PROCEDURES

Study visits will occur at Screening, Baseline/Day 1, and on-treatment at Weeks 2, 4, 8, and 12 (weeks 20 and 24 for 24 weeks treatment period subjects). Post treatment Visits will occur at Weeks 4, 12, and 24 following the last dose of study medications.

Information on the specific laboratory parameters to be measured and clinical assessments to be performed are described below and in **Appendix 1**.

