#### **6.3.1. Post Treatment Week 4 (+/- 7 days)**

The following procedures/assessments are to be completed for all subjects, 4 weeks after taking the last dose of study drugs:

- Perform a detailed medical history
- Assessment of AEs and concomitant medications
- Pregnancy prevention counseling
- Obtain body height and weight
- Obtain vital signs (resting blood pressure, pulse and temperature)
- Vasculitis activity score (Birmingham vasculitis score) for subjects with vasculitis.
- Glomerulonephritis evaluation (urine sample and serum creatinine sample) for subjects with glomerulonephritis
- ACR20-70 score (for subjects with Rheumatoid arthritis). This score includes a physical exam, a HAQ and a blood sample to evaluate ESR or CRP.
- Perform complete physical examination, including vasculitis, joint, neuropathy examination and sicca syndrome (for subjects with Sicca syndrome)
- Subject completes Health Assessment Questionnaire
- Obtain blood samples for:
  - Hematology profile
  - Chemistry profile
  - Coagulation profile
  - ESR and CRP
  - HCV RNA
  - Analysis of cryoglobulinemia measuring cryoglobulins, analyzing cross reactive idiotypes, analysis of complement, HCV core ELISA and FACS.
- Obtain urine sample for:
  - Urine pregnancy test
  - If a positive urine pregnancy test is reported, the subject will be asked to return to the clinic for a confirmatory serum pregnancy test.
  - Urinalysis and urine creatinine

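### The three early-stopping sections leave out the post-treatment Week 4 visit that other sections require of everyone, so a primary SVR4 sample can be missed

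*Combined protocol and SAP*

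**What the plan says.** Two sets of passages give the visits that follow the last dose.

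**Early stoppers.** Section 3.3: "All subjects who terminate treatment early will complete the early termination (ET) visit and post treatment 12 and 24 visits". Section 3.6: "All subjects who terminate treatment early will complete the Early Termination (ET) visit and post treatment 12 and 24 visits". Section 3.5 says that subjects who terminate early "will be asked to complete the (ET) visit and post treatment Week 12 visits and week 24". That sentence closes a list introduced by "Study drug(s) must be discontinued in the following instances", which has seven reasons. Only one of them is virologic failure.

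**Everyone.** Synopsis, Study Procedures/Frequency: "All subjects will complete the post treatment Week 4, 12 and 24 visits". Section 3.2: "All subjects will complete post treatment Week 4, 12 and 24 visits". Section 6: "Post treatment Visits will occur at Weeks 4, 12, and 24 following the last dose of study medications", with no exception, though without the words *all subjects*. Section 6.3.1 says that the Week 4 procedures, which include HCV RNA, "are to be completed for all subjects, 4 weeks after taking the last dose of study drugs". Section 6.3 times all three visits from the last dose, so Week 4 is well defined for a patient who stops early.

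The first primary objective (synopsis and Section 2) names SVR at 4 and at 24 weeks. Section 3.6 refers to Section 6.2.7 for the ET visit, but the body text ends its on-treatment visits at 6.2.5 and goes on to 6.3. Section 9 gives no analysis set and no rule for a missing SVR sample.

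**The concern.** The early-stopper list keeps Week 12, which the primary objective does not name, and drops Week 4, which it does. The same omission occurs in all three places that set follow-up for patients who stop early. It therefore reads as a deliberate shorter schedule, and a specific rule is commonly taken to override a general one.

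If staff follow it, a patient who stops for toxicity, intercurrent illness, pregnancy or another non-virologic reason has no HCV RNA at the SVR4 time point. That sample cannot be recovered later. Two safety duties also lose the visit that serves them: adverse event collection to 4 weeks after the last dose (Section 8.3) and the pregnancy test at 30 days (Section 6.4.8).

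**Working it through.** The conflict lies in the text, so the first step is to set the lists side by side.

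| Source | ET | Week 4 | Week 12 | Week 24 | Applies to |
|---|---|---|---|---|---|
| 3.3, 3.5, 3.6 | yes | not listed | yes | yes | early stoppers |
| Synopsis, 3.2 | – | yes | yes | yes | all subjects |
| 6 | – | yes | yes | yes | no exception stated |
| 6.3.1 | – | yes | – | – | all subjects |

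**Timing of the first HCV RNA after ET** (days from last dose; windows from 6.3.1 and 6.3.2)
- Week 4: 28 ± 7 = Day 21-35.
- Week 12: 84 ± 7 = Day 77-91.
- Gap after the 4-week AE window closes: 77 − 28 = 49 to 91 − 28 = 63 days.
- Gap after the 30-day pregnancy test date: 77 − 30 = 47 to 91 − 30 = 61 days.
- The Week 12 and 24 checklist names SAEs and no pregnancy test. The Week 4 checklist has AEs and the test.

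**Effect on SVR4.** Take N = 10 (Section 4.1), nine Week 4 responders and one early stopper without a Week 4 sample. Intervals are Clopper-Pearson 95%; for x = n the lower limit is 0.025^(1/n).
- (a) RNA below LLoQ at Weeks 12 and 24. If SVR4 may be inferred: 10/10 = 100% (69.2-100%). If the patient counts as a failure: 9/10 = 90% (55.5-99.7%). If the patient is excluded: 9/9 = 100% (66.4-100%). The plan does not choose among these.
- (b) Later RNA positive or absent. The true result is 9/10 or 10/10. A positive Week 12 result cannot show whether relapse came before or after Week 4.

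For scale, the only precision figure in Section 9 is a margin of about 15%. At 95%, 1.96 × √(p(1 − p)/10) gives 14.7 points at p = 0.94, so that figure implies an unstated SVR rate near 94%. The present point does not depend on it, but one patient is 10 points.

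**How often.** The documents give no early-stopping rate, so both p (early-stop rate) and q (share of early stoppers in case (b)) are assumptions.
- At least one early stopper: 1 − (1 − p)^10.
- At least one unresolved SVR4: 1 − (1 − pq)^10.

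| | p = 1% | p = 5% | p = 10% |
|---|---|---|---|
| Any early stopper (upper bound on harm) | 9.6% | 40.1% | 65.1% |
| Unresolved, q = 10% | 1.0% | 4.9% | 9.6% |
| Unresolved, q = 25% | 2.5% | 11.8% | 22.4% |
| Unresolved, q = 50% | 4.9% | 22.4% | 40.1% |

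**The case against.** The strongest reply is that the rules add up and do not conflict. The early-stopper sections do not say that their list is complete, no passage exempts early stoppers from Week 4, and doing all the visits satisfies every section. Section 3.2 also sends the reader to Section 6 and Appendix 1 for the assessments at each visit, and Section 6 includes Week 4. That reading is possible. But nothing in the body text directs a reader to it, and the reference that might have done so leads nowhere. The Appendix 1 tables were not available to this review and may settle the question.

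Several limits on the harm also stand:
- Patients stopped for virologic failure lose nothing on SVR4.
- Six of seven listed reasons is a count of reasons, not of risk. Some of them, such as a subject's request to stop, may end follow-up whichever list applies.
- Where later RNA is absent because the patient is lost, listing Week 4 might not have produced a sample, so not all of q is due to the omission.
- The AE and pregnancy-test duties remain in force. What is missing is a listed visit to carry them out.
- This is a descriptive pilot with wide intervals and no hypothesis test.

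These points make the effect smaller. They do not remove the mismatch between the visit lists.

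**Conclusion.** The point holds. Sections 3.3, 3.5 and 3.6 give a follow-up list without Week 4. The synopsis, 3.2 and 6.3.1 require that visit of all subjects, and Section 6 states it without exception. The omitted visit carries the sample for a primary time point.

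The consequence is conditional. It needs a patient who stops early for a non-virologic reason and staff who follow the shorter list. Each such patient leaves up to 10 percentage points of SVR4 open, and the number may be zero. Any probability of occurrence rests on assumed stopping rates. SVR24 is unaffected when its sample is taken. The inconsistency should be corrected, and before anyone stops early.

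**What to change.** 1. Reconcile Sections 3.3, 3.5 and 3.6 with the synopsis, 3.2, 6 and 6.3.1, so that early stoppers are listed for post-treatment Weeks 4, 12 and 24, timed from the last dose as in Section 6.3. Check that Appendix 1 agrees.
2. Correct the reference to Section 6.2.7 so that it points to where the ET assessments are listed.
3. Optionally, state in Section 9 that all treated patients form the SVR denominator and how a missing Week 4 HCV RNA is counted, for example as no SVR unless later HCV RNA settles it.

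The cost is wording in three sections, one cross-reference and, for each early stopper, at most one visit that Section 6.3.1 already describes. The optional sentence adds no procedure. The sample size stays at 10.
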